10.4.2 Electrocardiogram

10.4.2.1 Variable, Definition and/or Derivation

Electrocardiogram	Variables
Overall interpretation	Normality - Normal - Abnormal NCS - Abnormal CS
	Shift from baseline to week n, n=14, 26 - Normal or Abnormal NCS - Abnormal CS
	Shift from baseline to final visit - Normal or Abnormal NCS - Abnormal CS

10.4.2.2 Method of Analysis

For electrocardiography, the frequency and percentage by treatment group will be presented using the shift table for the changes in "normal or abnormal NCS" / "abnormal CS" before and after administration. In addition, the intragroup comparison will use McNemar's test, while the intergroup comparison (GV1001 0.56 mg/day vs. control group, GV1001 1.12 mg/day vs. control group) will use Pearson's chi-square test or Fisher's test to perform analysis.

Subjects with normal or abnormal NCS values at baseline that shifted to abnormal CS after baseline on electrocardiogram will be listed.

10.4.3 Physical Examination

10.4.3.1 Variable, Definition and/or Derivation

- Organ systems of physical examination: appearance, skin, head/neck, chest/lungs, heart, abdomen, urinary/genital system, extremities, musculoskeletal system, nervous system, and lymph nodes

10.4.3.2 Method of Analysis

Clinically significant result of physical examination will be listed.

11. SUBGROUP ANALYSES

Subgroup analyses for efficacy will be conducted on the endpoint related with PSP-rating scale, modified PSP-rating scale 10 and modified PSP-rating scale 14 for FAS using the same analysis methods (refer to 9.1 and 9.2).

Subgroup Variable	Category
PSP Type	
• Richardson type [PSP-RS]• Parkinsonian type [PSP-p]

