5. GENERAL CONSIDERATIONS FOR SUMMARIES AND ANALYSES

5.1 Significance Level

Unless otherwise specified, all statistical tests will be two-sided hypothesis tests performed at the 5% level of significance and all confidence intervals will be two-sided 95% confidence intervals.

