9.1.2 Method of Analysis

Descriptive statistics (number of subjects observed, mean, standard deviation, median, minimum, and maximum) will be presented by treatment group for each visit and the change from the baseline in the total score of the PSP-rating scale after 24 weeks (6 months) of investigational product administration. To test the difference between each study group and the control group (GV1001 0.56 mg/day vs. control group, GV1001 1.12 mg/day vs. control group), an MMRM analysis will be conducted with the treatment groups, visits, and interactions between the visits and the treatment groups set as fixed effects, and the subjects set as the random effect, as well as considering the baseline values, age, and sex as covariates. The results of the MMRM analysis will be summarized by LSM and standard error (SE) for each treatment group, the LSM difference between the study groups and the control group (GV1001 0.56 mg/day vs. control group, GV1001 1.12 mg/day vs. control group) and its 95% confidence interval as well as the two-side p-value.

Additionally, testing the difference within each treatment group will be conducted by the same MMRM analysis.

MMRM constructed as follows

- Dependent Variable: Change from baseline in total score of PSP-rating
- Fixed Effects
 - Fixed Continuous Effects: Baseline PSP-rating, Age
 - Fixed Categorical Effects: Treatment, Visit, Visit*Treatment, Sex
- Repeated Effect: Visit
- Random Effect: Subject
- Covariance Structure: Unstructured (UN)

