9.1.3 Interpret the Result

The Superiority of each study group to placebo is confirmed when the p-value for the interaction effect at 24 weeks is below 0.05.

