9.2 Secondary Efficacy Endpoint(s)

- 1) Change from the baseline in the total score of PSP-rating scale after 12 weeks (3 months) of investigational product administration
- 2) Change from the baseline in the Montreal Cognitive Assessment - Korea (MoCA-K) after 12 weeks (3 months) and 24 weeks (6 months) of investigational product administration
- 3) Change from the baseline in the Korean Frontal Assessment Battery (K-FAB) after 12 weeks (3 months) and 24 weeks (6 months) of investigational product administration
- 4) Change from the baseline in the England & Schwab Activity of Daily Living (ES ADL) scale after 12 weeks (3 months) and 24 weeks (6 months) of investigational product administration
- 5) Change from the baseline in the score of each domain of the PSP-rating scale after 12 weeks (3 months) and 24 weeks (6 months) of investigational product administration
- 6) Change from the baseline in the score of each item of the PSP-rating scale after 12 weeks (3 months) and 24 weeks (6 months) of investigational product administration
- 7) Change from the baseline in the total score of modified PSP-rating scale 10 after 12 weeks (3 months) and 24 weeks (6 months) of investigational product administration
- 8) Change from the baseline in the total score of modified PSP-rating scale 14 after 12 weeks (3 months) and 24 weeks (6 months) of investigational product administration
- 9) Proportion of subjects with change from the baseline in the total score of PSP-rating scale ≤ 0 after 24 weeks (6 months) of investigational product administration [Subgroup: Richardson type]
- 10) Proportion of subjects with change from the baseline in the total score of Modified PSP-rating scale 10 ≤ 0 after 24 weeks (6 months) of investigational product administration [Subgroup: Richardson type]
- 11) Proportion of subjects with change from the baseline in the total score of Modified PSP-rating scale 14 ≤ 0 after 24 weeks (6 months) of investigational product administration [Subgroup: Richardson type]

9.2.1 Change from the baseline in the total score of PSP-rating scale after 12 weeks (3 months) of investigational product administration

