11.2.5. Multiple Comparisons and Multiplicity

Given that this is a Phase 2 clinical study for therapeutic exploratory purposes, no correction of type I error due to comparisons with the control group were considered for each of the study groups (GV1001 0.56 mg/day, 1.12 mg/day).

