11.2.6. Subgroup Analysis

Subgroup analysis will not be considered in this clinical study.

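### SAP 11 tests treatment within each PSP type but never estimates whether the effect differs between types, so a result significant in one type only can be misread as type-specific

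*SAP*

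**What the plan says.** - **Protocol 11.2.6** planned none of this: "Subgroup analysis will not be considered in this clinical study". SAP 3.5 lists the subgroup analysis and five extra secondary endpoints as additions, with further exploration of efficacy as the reason.
- **SAP 11** applies to endpoints based on the PSP-rating scale and its two modified versions, in the FAS, by PSP type (PSP-RS and PSP-p), "using the same analysis methods (refer to 9.1 and 9.2".
- **SAP 9.1.2** gives the model. Its categorical terms are "Fixed Categorical Effects: Treatment, Visit, Visit*Treatment, Sex"; baseline score and age are the continuous terms. The model in 9.2 has the same structure.
- **SAP 9.1.3** adds a decision rule: "The Superiority of each study group to placebo is confirmed when the p-value for the interaction effect at 24 weeks is below 0.05". The only interaction in that model is visit by treatment, so this is not a treatment-by-type test.
- **SAP 5.1** states that "all statistical tests will be two-sided hypothesis tests performed at the 5% level of significance" unless otherwise specified. SAP 5.3 plans no stratification, and SAP 12 and 13 plan no sensitivity or additional analyses.
- **SAP 9.2.9 to 9.2.11** define responder endpoints, the first being "Proportion of subjects with change from the baseline in the total score of PSP-rating scale" at or below zero at Week 24. Each is labelled for the Richardson type. No version in all subjects is listed.

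**The concern.** Whether a drug works differently in two types of patient is a question about the difference between two treatment effects. Two separate tests, one per type, do not answer it. Each can fall on either side of 0.05 by chance, and the smaller type has less power even when the true effect is the same.

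The secondary objective is to gather information for deciding on later development and later studies. Whether to enrol both types or one is a natural question for such a study. A reader with a small p-value for PSP-RS and a large one for PSP-p could take the effect to be confined to PSP-RS. The planned output contains nothing that would show how weakly the data support that.

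**Working it through.** **Does any planned analysis give the between-type contrast?** SAP 11 points to 9.1 and 9.2. Those models have no type term, so applying them by type can only mean separate fits. The text does not say so outright, but no other reading fits. SAP 5.3, 12 and 13 add nothing. The contrast is therefore not estimated anywhere.

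**Inputs**
- From the documents: 20 evaluable subjects per arm, 1:1:1 allocation, two-sided 5% level. The plan's own sample-size figure reproduces: 20 / (1 − 0.20) = 25 per arm, and 3 × 25 = 75. No power, effect size, SD or subgroup size is given.
- Assumed: a PSP-RS share of 50% to 80%, equal across arms, and the same true effect in both types, in units of the SD of the Week 24 change. A two-sample t-test stands in for the Week 24 MMRM comparison.

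**Chance that one dose is significant in exactly one type.** Let a and b be the power in the two types, from the noncentral t distribution with noncentrality d × √(m/2), where m is the number per arm within the type. Then P = a(1 − b) + b(1 − a).

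| True effect, same in both types | PSP-RS : PSP-p per arm | a | b | P |
|---|---|---|---|---|
| 0 | any | 0.050 | 0.050 | 9.5% |
| 0.3 SD | 10 : 10 | 0.097 | 0.097 | 18% |
| 0.6 SD | 10 : 10 | 0.246 | 0.246 | 37% |
| 0.6 SD | 14 : 6 | 0.333 | 0.156 | 39% |
| 0.9 SD | 10 : 10 | 0.478 | 0.478 | 50% |
| 0.9 SD | 14 : 6 | 0.630 | 0.292 | 55% |

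For example, at 0.9 SD and 14 : 6, 0.630 × 0.708 + 0.292 × 0.370 = 0.554.

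A simulation with both doses and a shared control (60,000 runs per setting, PSP-RS share 50% to 80%) agrees. It gives 31% to 33% at 0.5 SD and 50% to 61% at 0.886 SD, the effect that gives 80% power overall at 20 per arm.

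**What the missing contrast would deliver.** For one dose against control, in SD units and by normal approximation, SE = √(2/n_RS + 2/n_P). The SE of the overall effect is √(2/20) = 0.316.

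| PSP-RS share | SE | Ratio to overall SE | 95% CI half-width (1.96 × SE) | Power for a between-type difference of 0.886 SD |
|---|---|---|---|---|
| 50% | 0.632 | 2.0 | 1.24 SD | 29% |
| 70% | 0.690 | 2.18 | 1.35 SD | 25% |
| 80% | 0.791 | 2.5 | 1.55 SD | 20% |

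**A related but separate figure.** With no effect anywhere, four tests on one endpoint (two doses by two types) give a chance of about 17% of at least one p below 0.05, allowing for the shared control. If the tests were independent it would be 1 − 0.95⁴ = 18.5%. This is multiplicity, and an interaction term does not cure it.

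**The case against.** The other side has several fair points.

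- **The trial is exploratory and the additions are declared.** SAP 3.5 lists them with a reason, so the departure from protocol 11.2.6 is not itself a defect. No passage says that the next study's population will be chosen from subgroup p-values. A reader might infer that a chance difference will be taken as real, but the documents support only that it can be. This stands.
- **The superiority rule.** A reader might infer that the SAP declares superiority within each type by 9.1.3. SAP 11 imports methods, and in 9.1 the method (9.1.2) and the interpretation (9.1.3) have separate headings. Because SAP 11 cites 9.1 as a whole, the carry-over is possible, but it is not stated. This stands as an ambiguity to close.
- **Convergence.** A reader might expect an unstructured covariance to fail in a small type. Protocol 10.3.12 schedules the PSP-rating scale after baseline only at Visits 10 and 16. The matrix is therefore 2 × 2, with three parameters, estimated from all three arms of a type together. Variances will be imprecise, but the documents give no ground for predicting failure.
- **The size depends on assumptions.** If the true effect is small, discordance is less frequent: about 18% at 0.3 SD and 9.5% with no effect. This stands.
- **Multiplicity.** Protocol 11.2.5 openly accepts that "no correction of type I error due to comparisons with the control group were considered for each of the study groups". The four-test figure belongs to that choice, although no statement covers the subgroups.
- **The contrast has low power.** This is true, and it is a reason to report an interval instead of relying on a test. It does not justify leaving the contrast out: a wide interval shows that the data cannot separate the types, and two separate p-values hide that.

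On the responder endpoints, SAP 11 could be read as extending 9.2.9 to 9.2.11 to PSP-p, since it covers endpoints related to the scale. Their own definitions name the Richardson type only.

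**Conclusion.** The gap is real. Neither document contains a treatment-by-type term, and no planned analysis estimates the difference in effect between PSP-RS and PSP-p.

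If the types respond alike, with a true effect of 0.6 to 0.9 SD and a 50:50 to 70:30 mix, a given dose will be significant in one type only in about 37% to 55% of trials. That range rests on an assumed mix and effect, 20 evaluable subjects per arm and a simplified test. The qualitative point, that within-type p-values do not measure a between-type difference, needs none of these assumptions.

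The point concerns what subgroup results can support. It does not affect the primary FAS comparison. It is worth correcting because the change is small and uses data already planned for collection.

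**What to change.** In SAP 11, before unblinding:

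1. Add one MMRM on the FAS with PSP type and its interactions with treatment, with visit, and with treatment by visit, keeping the existing covariates.
2. For each dose, report the Week 24 treatment-by-type contrast (dose minus placebo in PSP-RS, less dose minus placebo in PSP-p) with its 95% CI. Take the type-specific estimates and CIs from the same model.
3. State that within-type p-values are descriptive and that 9.1.3 does not apply to subgroups.
4. Show 9.2.9 to 9.2.11 in all subjects and in both types.

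The cost is SAP wording, one model and a few table columns, with no new data. The joint model shares covariate slopes, and by default the covariance, across types; the SAP should say so. The main downside is precision. With CI half-widths of about 1.24 to 1.55 SD and 20% to 29% power for a 0.886 SD difference, the contrast will restrain subgroup claims more often than settle them. The SAP should add that a non-significant interaction does not show that the types respond alike.

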12. SENSITIVITY ANALYSES

Sensitivity analysis will not be considered in this clinical study.

13. ADDITIONAL ANALYSES

Additional analysis will not be considered in this clinical study.

Appendix.

1. Mock-up Tables, Figures and Listings
2. modified PSP-rating scale calculations

1.0	18 Oct 2022	
Initial protocol
 
 Change of manufacturer of study drug Clarification of phrases on the collection of human-derived samples Clarification of phrases in order to conduct the final visit schedule of dropped out subjects according to Visit 16 Clarification of the labeling of the study drug and comparator (placebo) New establishment of section [13.9.2 Investigator's obligations]
1.1	30 Nov 2022	
[Revision according to the supplementary request from the Ministry of Food and Drug Safety]
 
 Clarification of Clinical study duration Exclusion Criteria 6): Change of the criteria related to tumor history prior to participation in the clinical study Exclusion Criteria 10): Clarification of wording of the contraceptive period and addition of the detailed criteria for menopause Added number of laboratory tests and pregnancy tests [Other changes] After deleting the contents of study sites and principal investigators, etc. in the protocol, add a phrase as "See Appendix" and change the relevant Appendix 1 Change of shelf life of study drug
2.0	15 Feb 2023	
 Extension of screening period: 2 weeks → 4 weeks Changes related to collecting human-derived samples 
 Change the number of cerebrospinal fluid collections: 3 times → 2 times (collection at Visit 10 deleted) Change from Visit 2 → Visit 1 Setting Visit 1 to allow separate visits for collecting human-derived samples Inclusion criteria 7): Change in guardian accompanying conditions Clarification of information and labeling of investigational product Dropout Criteria: Deletion of dropout criteria in case of major protocol violations Change in term of adverse events Revision of Appendix 1 due to changes in study sites, principal investigator, and sample analysis institution, etc.
2.1	18 May 2023	
 Inclusion criteria 7): Addition of a condition allowing companions other than the guardian when visiting study sites except for efficacy evaluation visits Added appearance descriptions of investigational drugs Addition of types of syphilis test Revision of Appendix 1 due to changes in the principal investigator, etc.
3.0	03 Aug 2023	
 Inclusion criteria 7): Deletion of the exceptional condition for accompanying guardian
4.0	22 Nov 2023	
 Inclusion criteria 7): Addition of a condition allowing companions other than the guardian when visiting study sites except for efficacy evaluation visits Added appearance descriptions of investigational drugs Addition of types of syphilis test Revision of Appendix 1 due to changes in the principal investigator, etc.
5.0	08 Dec 2023	
 Inclusion criteria 7): Deletion of the exceptional condition for accompanying guardian

5.1

15 Mar 2024

[figure not shown]
- 6.4. Blinding and Unblinding: Clarification of wording for person in charge of dilution and administration
- Addition of phrases regarding secondary use of human-derived samples, etc.

[Protocol Synopsis]

Clinical Study Sponsor	GemVax&KAEL Co., Ltd. [REDACTED]		
Item Name (Code Name)	GV1001	Main Ingredient	Tertomotide HCl
Clinical Study Title	
진행성 핵상 마비 환자를 대상으로 GV1001 0.56 또는 1.12 mg/day 피하 투여 시 질환의 중증도 개선 효과와 안전성을 탐색하기 위한 다기관, 무작위배정, 이중 눈가림, 위약 대조, 평행 설계, 전향적, 제2a상 임상시험
 
A Multi-center, Randomized, Double-blind, Placebo-controlled, Parallel design, Prospective, Phase IIa Exploratory Clinical Trial to evaluate the efficacy and safety of Subcutaneous Administration of GV1001 0.56 or 1.12 mg/day in Patients with Progressive Supranuclear Palsy
		
Clinical Study Identification No.	GV1001-PSP-CL2-011		
Coordinating Investigator	Professor [REDACTED], Department of Neurology, SMG-SNU Boramae Medical Center		
Study Sites and Principal Investigators	See [Appendix 1]. List of clinical trial participants and clinical trial pharmacists		
Clinical Study Duration	Approximately 24 months from the date of approval by the Ministry of Food and Drug Safety and the IRBs of study sites		
Target Disease	Progressive supranuclear palsy (PSP)		
Clinical Study Objectives	
[Primary Objective] To explore the efficacy and evaluate the safety of GV1001 0.56 mg/day or 1.12 mg/day administered for 24 weeks on the severity of disease in patients with progressive supranuclear palsy.
 
[Secondary Objectives] To collect source data to determine the possibility of progression to the next stage of development and to subsequent clinical studies by analyzing the clinical and biological parameters associated with the treatment response and safety information of 2 dose levels of GV1001, 0.56 mg/day or 1.12 mg/day, in patients with progressive supranuclear palsy.
		
Clinical Study Phase and Design	Multicenter, randomized, double-blind, placebo-controlled, parallel design, prospective, Phase 2a exploratory clinical study		
Target Number of Subjects	
This is a Phase 2a exploratory clinical study conducted for the purposes of collecting initial safety and efficacy information on the investigational product GV1001 in patients with progressive supranuclear palsy as well as providing the basis for design, evaluation items, and evaluation methods for subsequent clinical studies.
 
This is an exploratory study to estimate the clinically significant effect size to demonstrate the efficacy of this investigational product in patients with progressive supranuclear palsy. Accordingly, the number of subjects was not calculated based on statistical considerations, and it is intended to set 20 subjects per group since the minimum number of subjects required in a pilot study is 12 subjects²¹⁾ and approximately 30 subjects can be considered according to the rule of thumb^{22), 23)}. Furthermore, considering a dropout rate of 20%, a total of 75 subjects with 25 subjects per group will be enrolled.
		

Investigational Product	
 • Study drug: 
 - Study drug 1: GV1001 0.84 mg/vial - Study drug 2: GV1001 1.68 mg/vial • Comparator: 
 - Placebo of GV1001
Method and Duration of Investigational Product Administration	
The study drug or the placebo will be administered once weekly for the first 4 weeks (1 month), and then administered 10 times at 2-week intervals for 20 weeks (5 months) for a total of 14 subcutaneous doses over 24 weeks (6 months).

Inclusion Criteria	
 1) Patients aged ≥ 41 years to ≤ 85 years 2) Patients clinically diagnosed with a probable PSP (Richardson type [PSP-RS] or parkinsonian type [PSP-p]) by the diagnostic criteria for PSP developed by the International Parkinson and Movement Disorders Society Task Force 3) In the case of the PSP-RS type, patients with clearly identified supranuclear ophthalmoplegia (SOP) according to the judgment of the investigator (e.g., the sum of scores in the ocular motor part of the PSP-rating scale must be ≥ 5 points or the downgaze [voluntary downward command movement] score must be ≥ 2 points). In the case of the PSP-p type, patients identified as having shown little or no response to previous administration of levodopa according to the judgment of the investigator during the course of treatment 4) Patients who had been taking a stable dose of a neurological drug for at least 1 month prior to screening without changes in the dose 5) Patients who are able to walk 3 meters or more independently or with assistive devices 6) Patients with at least 15 points on the Korean Mini-Mental State Examination (K-MMSE) at the screening visit (However, the results of a test performed at the study site within 2 weeks prior to the screening visit may be used if available.) 7) Patients who have a guardian who can accompany the patient at all visits according to the schedule of this clinical study, and who is able to supervise the subject's compliance with the test and examination procedures performed at the visits and provide information on the subject's indication, and whose guardians have provided a written consent for participation in the clinical study 8) Patients and/or their representatives who have voluntarily provided a written consent for participation in this clinical study
Exclusion Criteria	
 1) Patients who fall under any of the following based on the CT/MRI scan results and neurological examinations performed within 12 months of screening or at screening 
 - Presence of structural lesions (vascular, neoplastic, inflammatory, infectious, demyelinating, etc.) that can clinically affect the patient's symptoms of progressive supranuclear palsy on brain CT or MRI - Suspected concurrent onset of central nervous system diseases* other than progressive supranuclear palsy that, according to clinical judgment, can cause parkinsonism 
 *Dementia or motor disorders due to vascular brain disease, subdural hematoma, normal pressure hydrocephalus, brain tumor, Alzheimer's disease, multiple system atrophy, Creutzfeldt-Jakob disease, etc. 2) Patients with a history of known or suspected seizures (including febrile seizure) 3) Patients with a recent unexplained loss of consciousness within 3 months prior to screening or a history of significant head trauma with loss of consciousness 4) Patients with acute or unstable cardiovascular disease, uncontrolled hypertension (exceeding 160/100 mmHg), uncontrolled diabetes (insulin-dependent or HbA1c

	
>8%), or any other medical condition that can interfere with completing the clinical study
 
5) Patients with hypersensitivity reactions to the ingredients of the investigational product
 
6) Patients with a history of cancer within 5 years prior to screening (however, nonmetastatic basal cell carcinoma of the skin, squamous cell carcinoma of the skin, carcinoma in situ of the cervix, or nonprogressive prostate cancer are allowed)
 
7) Patients with abnormal renal function (creatinine clearance [CLcr] < 30 mL/min on screening test)
 
8) Patients with severe liver function abnormalities (ALT or AST is ≥2.5 times the upper limit of normal on screening test)
 
9) Patients weighing ≤35 kg
 
10) The woman of childbearing potential and male subjects who do not agree to contraception using medically acceptable methods (surgical sterilization, intrauterine contraceptive device, tubal ligation, double-barrier methods [combined use of barrier methods such as male condoms, female condoms, cervical caps, contraceptive diaphragms, and contraceptive sponges]), a single-barrier method with spermicide, and complete abstinence) during the clinical study and up to 90 days after the end (discontinuation) of their participation in the clinical study.
 
However, women who have gone through menopause* or women or men who have undergone surgical sterilization (vasectomy, bilateral tubal ligation, etc.) before participating in the clinical study can participate even if they do not agree to contraception.
 
* In this clinical study, menopause is defined as one or more of the following.
 
(1) Female subjects aged ≥55 years who have had amenorrhea for more than 1 year
 
(2) Female subjects aged ≥41 years to <55 years who have had amenorrhea for more than 1 year and have a serum follicle stimulating hormone (FSH) level ≥ 30 mIU/mL
 
(3) In case of artificial menopause caused by bilateral oophorectomy
 
11) Pregnant or breastfeeding women
 
12) Patients who participated in another clinical study within 4 weeks prior to screening and were administered investigational products or were applied investigational medical devices
 
13) Patients who were administered the study drug (GV1001) of this clinical study within 12 months prior to screening
 
14) Patients who participated in a clinical study for progressive supranuclear palsy within 6 months prior to screening
 
15) Other patients judged by the investigator as ineligible to participate in this clinical study

Clinical Study Methodology	
This is a 24-week, multicenter, randomized, double-blind, placebo-controlled, parallel design, prospective, Phase 2a exploratory clinical study.
 
If the subject and/or the subject's representative provide a written consent to participate in this clinical study, the required examinations and tests will be performed at the screening visit, and the screening period will run for 4 weeks or shorter.
 
Subjects who are ultimately determined as eligible by the inclusion/exclusion criteria after screening will be randomized at a 1:1:1 ratio to Study Group 1 (GV1001 0.56 mg/day), Study Group 2 (GV1001 1.12 mg/day), or the placebo group depending on the study site in which they are enrolled. Depending on the randomization results, subjects will be administered the investigational product (study drug or placebo) once weekly for the first 4 weeks (1 month), and then administered 10 times at 2-week intervals for 20 weeks (5 months) for a total of 14 doses over 24 weeks (6 months).

	
All subjects will visit the study site according to the planned clinical study schedule to receive the investigational product and to be evaluated for efficacy and safety. To ensure the objectivity and accuracy of the study results, the efficacy evaluators evaluating the PSP-rating scale will be limited to neurologists who have been sufficiently educated and trained, and the collection of efficacy and safety evaluation data and biomarkers will be performed in a consistent order at each visit.
 
※ Neurological drugs administered at a stable dose for at least 1 month prior to a subject's participation in this clinical study (prior to screening) will be continued without changing the dose during the clinical study participation period.
  
SCR = Screening IP = Investigational Product EOT = End of Treatment EOS = End of Study

Endpoints and Evaluation Method	
[Primary Efficacy Endpoint] Change from the baseline in the total score of PSP-rating scale after 24 weeks (6 months) of investigational product administration
 
[Secondary Efficacy Endpoints]
 
 1) Change from the baseline in the total score of PSP-rating scale after 12 weeks (3 months) of investigational product administration 2) Change from the baseline in the Montreal Cognitive Assessment - Korea (MoCA-K) after 12 weeks (3 months) and 24 weeks (6 months) of investigational product administration 3) Change from the baseline in the Korean Frontal Assessment Battery (K-FAB) after 12 weeks (3 months) and 24 weeks (6 months) of investigational product administration 4) Change from the baseline in the England & Schwab Activity of Daily Living (ES ADL) scale after 12 weeks (3 months) and 24 weeks (6 months) of investigational product administration 5) Change from the baseline in the score of each domain of the PSP-rating scale after 12 weeks (3 months) and 24 weeks (6 months) of investigational product administration 6) Change from the baseline in the score of each item of the PSP-rating scale after 12 weeks (3 months) and 24 weeks (6 months) of investigational product administration

	
[Exploratory Endpoints]
 
1) Change from the baseline in total tau (t-tau), phosphorylated tau (p-tau), and neurofilament light chain (NfL) markers in blood after 12 weeks (3 months), and in blood and cerebrospinal fluid after 24 weeks (6 months) of the investigational product administration2) Change from the baseline in inflammatory cytokine markers (IL-6, IL-8, IL-2, IFN- γ, TNF-α, etc.) in blood after 12 weeks (3 months), and in blood and cerebrospinal fluid after 24 weeks (6 months) of the investigational product administration3) Change from the baseline in blood after 12 weeks (3 months), and in blood and cerebrospinal fluid markers after 24 weeks (6 months) of investigational product administration, and correlation between clinical markers and treatment responses 
[Safety Endpoints]
 
1) Adverse events2) Laboratory tests (hematology test, blood chemistry test, urinalysis)3) Vital signs4) Electrocardiogram
--	--

[Clinical Study Schedule]

Period	Screening	Double blind treatment phase												Follow Up		
		1	2	3	4	6	8	10	12	14	16	18	20	22	24	26
Week	~4	1	2	3	4	6	8	10	12	14	16	18	20	22	24	28
Visit	1	2	3	4	5	6	7	8	9	10	11	12	13	14	15	17
Visit window (days)	-	-	-	-	-	-	-	-	-	-	-	-	-	-	EOT	EOS
															±5	±5
Subject Consent and Assignment of Screening Number	○															
Demographic Information	○															
Checking Medical/Surgical History	○															
Checking prior/concomitant medications	○															
Physical examination	○															
Vital signs	○															
Weight	○															
Height	○															
Electrocardiography ^[1]	○															
Laboratory tests ^[2]	○															
Urine hCG ^[3]	○															
Checking inclusion/exclusion criteria	○															
Randomization	○															
K-MMSE ^[4]	○															
PSP-rating scale	○															

Period	Screening										Double blind treatment phase										Follow Up	
	Week	~4	1	2	3	4	6	8	10	12	14	16	18	20	22	24	26	28				
Visit	1	2	3	4	5	6	7	8	9	10	11	12	13	14	15	16	17	EOS				
Visit window (days)	-	-	-	-	-	-	±3	±3	±3	±3	±3	±3	±3	±3	±3	±3	±3	±3	±5	±5	±5	±5
MoCA-K		○									○								○			
K-FAB		○									○								○			
ES ADL		○									○								○			
Brain CT ^[2]		(○)																				
Collecting human-Serum derived samples ^[6]	DNA, Plasma, Cerebrospinal fluid	○									○								○			
Investigational product administration ^[7]		○	○	○	○	○	○	○	○	○	○	○	○	○	○	○	○	○	○	○	○	
Adverse Event Assessment ^[8]		○	○	○	○	○	○	○	○	○	○	○	○	○	○	○	○	○	○	○	○	

[1] Electrocardiography: For the Visit 1 (screening) test, the results of a test performed within 3 months may be used if available, and retesting may be performed only once at the discretion of the investigator.

[2] Laboratory tests: For the Visit 1 (screening) tests, the results of tests performed within 4 weeks may be used if available, and retesting may be performed only once at the discretion of the investigator. At Visit 1 (screening), the serum FSH tests shall be performed to confirm menopause in women aged ≥ 41 years to < 55 years who have experienced amenorrhea for more than 1 year.

· Hematology test: WBC, RBC, Hemoglobin, Hematocrit, Platelets count, WBC differential count (Neutrophils, Lymphocytes, Monocytes, Eosinophils, Basophils)

· Blood chemistry test: BUN, Creatinine, Uric acid, Total bilirubin, Albumin, Total Protein, ALT, AST, γ -GTP, Alkaline phosphatase, Glucose, Total Cholesterol, HbA1c (performed only at screening visit)

· Serum Follicle Stimulating Hormone test: FSH (Performed only at screening visit for those who require confirmation of menopause)

· Urinalysis: Protein (Albumin), Glucose, Ketones, WBC, Blood (RBC)

· Blood coagulation test: INR (performed only at screening visit)

· Thyroid test: TSH, free T4 (performed only at screening visit)

· Syphilis, AIDS tests: VDRL or RPR, anti-HIV (performed only at screening visit)

· Serum creatinine clearance will be confirmed using the Cockcroft-Gault formula. (performed only at screening visit)

· Serum creatinine $CLcr = [(140 - \text{Age (years)} \times \text{Weight (kg)} \times 0.85 \text{ (for female subjects)} / 72 \times \text{Serum Creatinine (mg/dl)}$

[3] Urine hCG: Urine hCG pregnancy tests will be performed only for women of childbearing potential, excluding subjects confirmed to have undergone surgical sterilization and as being menopausal. However, for Visit 1 (screening), the subjects who performed the serum FSH test to confirm menopause when participating in the clinical study will also perform urine hCG pregnancy test

[4] K-MMSE: The results of a test performed at the study site within 2 weeks prior to the screening visit may be used if available.

[5] Brain CT: This will be performed only on subjects without brain CT imaging within 12 months prior to the screening visit

[6] Collecting human-derived samples: Human-derived samples (DNA, plasma, serum, and cerebrospinal fluid) will be collected for exploratory evaluations, and they will be transferred to the central lab for analysis and storage. However, in the case of cerebrospinal fluid, it will be collected only from subjects who have separately consented to collection of samples. For Visit 1 (screening), separate visits for collecting human-derived samples can be set up and implemented within the screening period.

[7] Investigational product administration: Subjects will be observed for approximately 20 minutes after the administration of the investigational product from Visit 2 to Visit 1.5.

[8] Adverse events assessment: Adverse events that occurred after the first administration of the investigational product will be identified, and prior to the first administration, it will be collected as medical history.

[Abbreviations and Terms]

Abbreviation	Full term
ADR	Adverse Drug Reaction
AE	Adverse Event
AIDS	Acquired Immune Deficiency Syndrome
ALT	Alanine Aminotransferase
ANOVA	Analysis of Variance
AST	Aspartate Aminotransferase
BUN	Blood Urea Nitrogen
CRO	Contract Research Organization
EOS	End of Study
EOT	End of Treatment
ES ADL	England & Schwab Activity Of Daily Living
FAS	Full Analysis Set
FSH	Follicle Stimulating Hormone
GCP	Good Clinical Practice
HbA1c	Hemoglobin A1c
hCG	human Chorionic Gonadotropin
IDMC	Independent Data Monitoring Committee
IFN	Interferon
IL	Interleukin
INR	International Normalized Ratio
IRB	Institutional Review Board
IWRS	Interactive Web Response System
K-FAB	Korean Frontal Assessment Battery
KGCP	Korean Good Clinical Practice
K-MMSE	Korean Mini-Mental State Examination
LSM	Least Squares Mean
MedDRA	Medical Dictionary for Regulatory Activities
MMRM	Mixed-Effect Model Repeated Measure
MoCA-K	Montreal Cognitive Assessment-Korean Version
NfL	Neurofilament-Light chain
PPS	Per-Protocol Set
PSP	Progressive Supranuclear Palsy
PSP-p	Progressive Supranuclear Palsy-parkinsonism
PSP-RS	Progressive Supranuclear Palsy-Richardson's Syndrome
PT	Preferred Term
p-Tau	phosphorylated Tau
RBC	Red Blood Cell
RPR	Rapid Plasma Reagin
SAE	Serious Adverse Event
SE	Standard Error
SOC	System Organ Class
SOP	Standard Operating Procedure
SOP	Supranuclear Ophthalmoplegia
SUSAR	Suspected Unexpected Serious Adverse Reaction
TEAE	Treatment-Emergent Adverse Event
TNF	Tumor Necrosis Factor
TSH	Thyroid Stimulating Hormone
t-Tau	total Tau
VDRL	Venereal Disease Research Laboratory
WBC	White Blood Cell
γ -GTP	gamma-Glutamyl Transpeptidase

1. Clinical Study Title and Phase

